13.4 Post Treatment

Post treatments depend on investigator's choice.

14. Efficacy Assessment

14.1 Assessment of Antitumor Efficacy (RECIST Guideline Version 1.1)

14.1.1 Evaluation of lesions

14.1.1.1 Measurement of Lesions

The diameters of individual lesions, the long axis for non-nodal lesions and the short axis for nodal lesions, should be measured (in mm) using objective diagnostic techniques.

14.1.1.2 Tumor Definitions

(1) Measurable Lesions

Measurable tumor lesions: Lesions that can be accurately measured in at least 1 dimension with the longest diameter (to be recorded) ≥ 10 mm by CT or MRI scan if using slice thickness of 5 mm or less, or at least double the slice thickness of CT or MRI scan if the slice thickness is >5 mm.

Measurable malignant lymph nodes: A lymph node must be considered pathologically enlarged with high suspicion of metastasis and measure ≥ 15 mm in the short axis when assessed by CT or MRI scan. The short axis is defined as the longest linear dimension perpendicular to the node's longest diameter as assessed within the same plane that the scan was acquired.

Only measurable lesions can be selected as target lesions.

(2) Non-measurable Lesions

Non-measurable lesions include:

- Small metastatic tumor lesions that have a longest dimension less than 10 mm or if slice thickness is greater than 5 mm less than twice the slice thickness.
- Abnormal and suspected metastatic lymph nodes that are ≥ 10 mm to <15 mm in the short axis.
- Truly non-measurable lesions (e.g., ascites).
- Primary lesion (in case primary lesion is not able to be evaluated as non-measurable lesion, evaluation of the lesion will not be performed.)

All non-measurable lesions can only be selected as non-target lesions.

(3) Target Lesions

- All measurable lesions up to a maximum of 2 lesions/organ and 5 lesions in total, representative of all involved organs should be identified as target lesions.
- Target lesions should be selected on the basis of their size (visceral lesion with the longest diameter and lymph node with the measurement of short axis), be representative of all involved organs, but in addition should be those that lend themselves to reproducible repeated measurements.
- When recording tumor measurements the longest diameter will be measured for

tumor lesions. For pathological lymph nodes, the short axis will be measured.

- Lymph nodes identified as target lesions should always have the actual short axis measurement recorded, even if the nodes regress to below 10mm on study. This means that when lymph nodes are included as target lesions, the sum of lesions may not be zero even if complete response (CR) criteria are met.
- The sum of the diameters for all target lesions at baseline will be calculated as the baseline sum. The baseline sum will be used as a reference for follow-up tumor assessment.
- An option of ‘Not Assessable’ for a lesion will only apply to lesions that cannot be read due to technical reasons, for example:
 - CT artifact.
 - Patient positioning where the lesions are obstructed or cannot be seen.
 - Lesion that may not be seen in their entirety due to CT slice thickness.
- In cases where a lesion divides into 2 lesions, the longest diameters of the fragmented portions should be added together to calculate the target lesion sum.
- In cases where 2 lesions coalesce, a plane between them may be maintained that would aid in obtaining maximal diameter measurements of each individual lesion. If the lesions have truly coalesced such that they are no longer separable, the vector of the longest diameter in this instance should be the maximal longest diameter for the ‘coalesced lesion’.

(4) Non-target Lesions

- Non-target lesions include all non-measurable lesions and measurable lesions that have not been selected as target lesions.
- Lymph nodes that have a short axis <10 mm are considered non-pathological and should not be recorded.
- All lesions (or sites of disease) other than target lesions, including pathological lymph nodes, should be identified as non-target lesions and should also be recorded at baseline. Measurements are not required, but their presence, absence, or unequivocal progression should be followed until tumor follow-up discontinuation.
- It is possible to record multiple non-target lesions involving the same organ as a single item on the eCRF (e.g., multiple enlarged pelvic lymph nodes or multiple liver metastases).

14.1.1.3 Evaluation of Response in Target Lesions

The response in target lesions should be evaluated using the 5-grade scale shown below.

Complete Response (CR):

Complete disappearance of non-nodal target lesions, and the short axes of all nodal target lesions below 10 mm (an assessment of CR with the sum of diameters being above 0 is possible if nodal lesions have been included in target lesions before the study treatment).

Partial Response (PR):

A decrease of at least 30% in the sum of the diameters of target lesions in comparison with the baseline value.

Stable Disease (SD):

The absence not only of tumor shrinkage corresponding to CR or PR but also of tumor growth corresponding to PD.

Progressive Disease (PD):

An increase of at least 20% and at least 5 mm in length in the sum of the diameters of target lesions in comparison with the smallest value among the sums obtained previously (including the baseline value).

Not Evaluable (NE):

Lack of examination for any reason; response corresponding to none of CR, PR, SD, and PD.

The diameters of target lesions should have their actual measurements recorded even when they have become very small (e.g. 2 mm). When the diameter has become “too small to measure”, the measurement should be recorded as 0 mm if the lesion is considered to have disappeared, or a default value of 5 mm should be assigned if the lesion is believed to be present.

14.1.1.4 Evaluation of Response in Non-Target Lesions

The response in non-target lesions should be evaluated using the 4-grade scale shown below.

Complete Response (CR):

Complete disappearance of non-nodal non-target lesions, the short axes of all nodal non-target lesions below 10 mm, and all tumor marker levels at or below the institutional upper normal limits.

Non-Complete Response/Non-Progressive Disease (Non-CR/non-PD):

The presence of at least one non-nodal non-target lesion; or the short axis not less than 10 mm in at least one nodal non-target lesion; or any tumor marker levels above the institutional upper normal limits.

Progressive Disease (PD):

Clear progression of existing non-target lesions, where “clear progression” is, in the presence of target lesions, an increase in overall tumor volume which is assessed as warranting discontinuation of the study treatment despite SD or PR in the target lesions but does not apply to a “modest increase” in tumor volume, and in the presence of only non-measurable lesions, e.g. a 73% increase in tumor volume (equivalent to a 20% increase in the diameters of measurable lesions).

Not Evaluable (NE):

Lack of examination for any reason; response corresponding to none of CR, Non-CR/non-PD, and PD.

Examination of Pleural, Ascitic, and Pericardial Fluids: Any fluid in body cavities that has collected or increased in the absence of progression in both target and non-target lesions should be examined for cytology as needed, and assessed to determine whether its collection/increase represents an adverse event or PD.

Although this protocol specifies no procedures for confirmation of the appearance of new lesions, it is advisable that any findings suggesting development of new lesions be promptly investigated using appropriate diagnostic instruments.

14.1.2 Assessment of Overall Response

Assessments will be based on the definitions provided in Table 14.1.2-1 and Table 14.1.2-2 below.

Table 14.1.2-1 Time Point Response for Patients with Target (+/- Non-target) Disease

Target Lesions	Non-target Lesions	New Lesions	Overall Response
CR	CR	No	CR *
CR	Non-CR/Non-PD or Not all evaluated	No	PR
PR	Non-PD or Not all evaluated	No	PR
SD	Non-PD or Not all evaluated	No	SD
Not all evaluated	Non-PD	No	NE
PD	Any	Yes or No	PD
Any	PD	Yes or No	PD
Any	Any	Yes	PD

* For CR, tumor marker must have been under upper limit of normal.

Table 14.1.2-2 Time Point Response for Patients with only Non-target Disease

Non-target Lesions	New Lesions	Overall Response
CR	No	CR *
Non-CR/Non-PD	No	Non-CR/Non-PD
Not all evaluated	No	NE
Unequivocal PD	Yes or No	PD
Any	Yes	PD

* For CR, tumor marker must have been under upper limit of normal.

When no imaging/measurement is done at all at a particular time point, the patient is not evaluable (NE) at that time point. If only a subset of lesion measurements are made at an assessment, usually the case is also considered NE at that time point, unless a convincing argument can be made that the contribution of the individual missing lesion(s) would not

change the assigned time point response.

14.1.3 Best Overall Response Assessment

The best overall response as per RECIST Criteria (version 1.1) is the best response recorded from the start of the study treatment until the end of tumor follow-up period. The confirmation of tumor response for CR or PR is not required, but the duration of SD (or Non-CR/Non-PD) is set as 6 weeks from randomization (the data may be collected within 1 week before or after the scheduled date).

14.2 Overall Response Rate (ORR)

ORR is defined as the proportion of patients with the best overall response of CR or PR in tumor response evaluable population.

14.3 Disease Control Rate (DCR)

The assessment of DCR will parallel that of ORR, with DCR defined as the proportion of patients with objective evidence of CR, PR, or SD.

14.4 Progression Free Survival (PFS)

Progression free survival is defined as the time (in months) from the date of randomization until the date of the investigator-assessed radiological disease progression or death due to any cause, whichever comes first. Patients who receive post treatment before disease progression will be censored at the date of the last evaluable tumor assessment before post treatment is initiated. Patients who are alive with no disease progression at the time of the analysis will be censored at the date of the last confirmation as non-PD.

Event / Censoring	Case	Event date
Event	PD	the date of disease progression
	Death (without PD)	the date of death
Censoring	Non-PD at the time of analysis	the date of the last tumor assessment
	The date of PD is unknown	the date of the last tumor assessment
	Patient without any tumor assessment after randomization	the date of randomization
	Patient receive other post treatment for a reason other than PD	the date of the last tumor assessment
	Other	the date of the last tumor assessment

14.5 Time to Treatment Failure (TTF)

Time to treatment failure is defined as the time from the date of randomization until the date of last dose of study treatment. Patients who are still on study treatment as of the cut-off date will be censored at the last date of study treatment, or the cut-off date, whichever is earlier.

14.6 Overall Survival (OS)

Survival is defined as the time from the date of randomization to the date of death due to any cause. In the absence of death confirmation or for patients alive as of the cut-off date, patient will be censored at the date of last study follow-up, or the cut-off date, whichever is earlier.

15. Reporting Safety Information

15.1 Adverse Events/Serious Adverse Events

15.1.1 Adverse Events

An adverse event (AE) is any untoward medical condition that occurs in a patient while participating in a clinical study and does not necessarily have a causal relationship with the use of the product.

Treatment emergent adverse events are AEs that occur from the initiation of any study medication administration, and do not necessarily have a causal relationship to the use of the study medication.

Provide a complete and specific clinical diagnosis as an AE term. If a diagnosis is not available, then report physical examination. The National Cancer Institute Common Terminology Criteria for Adverse Events (NCI CTCAE version 4.03) terms are to be used to assess severity/provide the grade for each adverse event that is reported.

Refer to Sections 15.1.5 and 15.1.6 for definitions and reporting of pregnancy, medication errors, and overdose, respectively.

Symptoms or laboratory or instrumental (e.g., electrocardiographic) abnormalities of a pre-existing disease, such as cancer or other disease, should not be considered an AE. However, occurrences of new symptoms as well as worsening of pre-existing medical conditions are considered AEs. In addition, a new laboratory or instrumental abnormality that has a clinical impact on a patient (e.g., resulting in study medication dose reduction, treatment delay, treatment discontinuation, requires treatment due to abnormal values, or is considered medically important by the investigator) is considered an AE, unless it is considered part of clinical manifestations to a clinical diagnosis that is already reported as an AE.

AEs will be reported from the time a patient signs informed consent through the period of patient follow-up (30 days after the last dose of study medication or until the start of new anti-tumor therapy, whichever is earlier). Document all AEs in the source documents. Documentation should include onset and resolution dates, severity/grade, relationship to study medication, and outcome of the event.

Any untoward medical event that occurs outside the period of patient follow-up (30 days after the last dose of study medication or until the start of new antitumor therapy, whichever is earlier) is not considered an AE. If any AEs are observed after the patient follow-up period has ended, only those AEs determined to have a causal relationship with the investigational drug will be recorded in the case report form.

Causal relationship:

- (1) Related: The AE is related if it follows a reasonable temporal sequence from administration of study medication.
- (2) Not related: The AE is not related when there is no reasonable possibility that the study medication caused the event. For the purposes of safety reporting, “no

reasonable possibility” means there is no evidence to suggest a causal relationship between the drug and the adverse event and one or more of the following conditions are true:

- Disease Under Study
- Medical Condition(s)
- Previous or Concomitant Medication
- Protocol-related Procedure
- Other

Outcome:

- Resolved without sequelae
- Resolved with sequelae
- Resolving (Should be used only in the reporting SAE)
- Unresolved
- Death
- Unknown

Any ongoing AEs should be followed until the earliest occurrence of one of the following:

- AE has resolved
- Although the AE has not yet resolved, the Investigator considers that the AE is stable or no further improvement is expected. An AE cannot be considered stabilized while the patient is on study medication. Ongoing AEs must be assessed for stabilization 30 days post after the last dose of study medication
- The start of new anti-tumor therapy
- Patient meets one of the survival follow-up discontinuation criteria
- Safety follow-up becomes impossible due to changing hospital or other reasons
- Patient wishes to discontinue the safety follow up (including withdrawal of consent)

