10.1.3.3 Criteria for Dose Reduction (Arm A)

If the patients suffered any adverse drug reaction that meets any of the following dose reduction criteria, a new treatment cycle will be started after confirmation that the subject meets “Section 10.1.3.1 criteria for dose initiation in each cycle”, with the dose of TAS-118 or L-OHP reduced 1 level in each step according to the scheme for dose reduction criteria. Dose reduction is not allowed in the same treatment cycle.

Table 10.1.3.3-1 Dose reduction criteria for TAS-118 and L-OHP

Item	Criterion	TAS-118	L-OHP
Neutrophil count	< 500/mm ³ (Grade 4)	Worst grade observed in last cycle	1 step
Platelet count	< 25000/mm ³ (Grade 4)		1 step
Febrile neutropenia	Grade 3 ≤		1 step
Stomatitis	Grade 3 ≤		1 step
Diarrhea	Grade 3 ≤* ¹		1 step
Peripheral sensory neuropathy	Grade 3 ≤* ²		-
Serum creatinine	1.2 - < 1.5 mg/dL	The value observed before the initiation of new treatment cycle	1 step
Others* ³	Difficulty in continuing treatment without reducing the study drug dose as assessed by the investigator (subinvestigator)		

*1: In the event of a Grade 3 or greater adverse drug reaction in spite of the best treatment possible.

*2: Even if the grade is ≤ 2, the dose can be reduced at the investigator’s discretion.

*3: If the patient suffers from anorexia or other remarkable adverse drug reactions, the dose can be reduced at the investigator’s discretion.

Table 10.1.3.3-2 Dose reduction scheme for TAS-118 and L-OHP

Investigational product	Initial dose	Step 1	Step 2	Step 3
TAS-118	60 mg/dose	50 mg/dose	40 mg/dose	30 mg/dose
	50 mg/dose	40 mg/dose	30 mg/dose	None*
	40 mg/dose	30 mg/dose	None*	None*
L-OHP	85 mg/m ²	65 mg/m ²	50 mg/m ²	None*

* : In this case, the dose reduction cannot be done for the subjects, but there is no necessity that the study treatment is terminated. After confirmation that the patients meet all of dose resumption criteria, the study treatment can be restarted at minimum dose.

Table 10.1.3.3-3 Reduced dose of administration for TAS-118

Dosage in each dose	Number of sachet package	Total daily dose (Number of sachet packages)
30 mg	Morning: 1 Evening: 1	60 mg (2)
40 mg	Morning: 1 Evening: 1	80 mg (2)
50 mg	Morning: 1 Evening: 1	100 mg (2)

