15.1.2 Adverse Drug Reactions

Adverse drug reactions are concern noxious and unintended responses to a medicinal product within adverse events.

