16.3.3.3 Safety Analyses

Following analyses will be performed in AT population. However, same analyses will be done in FAS population if AT population doesn't correspond to FAS population.

(1) Adverse event

- Rate of adverse event will be summarized.
- For maximum grade of each adverse event in each patient, the number of patient and rate of adverse event by grade will be summarized.
- For all adverse events between onset of study drug administration and end of the trial, tables of their class, grade, onset date, causal relationship, outcome and treatment contents will be described.

(2) Adverse drug reaction

- For adverse drug reaction, same analyses as adverse events will be performed.

(3) Laboratory test

- Transition of main hematological laboratory values (White Blood Cell, Lymphocyte, Neutrophil, Hemoglobin, Platelet) at each point of each patient will be described as graph.

(4) Clinical findings

- For clinical findings (stomatitis, anorexia, diarrhea, peripheral sensory neuropathy), onset date of each patient, date of occurrence for maximum grade, first date of condition with grade 3 or higher, and time to recovery will be presented as list in each study treatment arm.

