5.1.2. Safety Endpoints

5.1.2.1 Adverse Events and Adverse Drug Reactions

An adverse event (AE) is any untoward medical condition sign, symptom, or disease that occurs in a subject while participating in this study and does not necessarily have a causal relationship with the study drug.

Treatment-emergent adverse events are AEs that occur from the initiation of any study medication administration and do not necessarily have a causal relationship with the study drug.

Any untoward medical sign, symptom, or disease that occurs outside the period of safety follow-up (30 days after the last dose of study medication or until the start of new antitumor therapy, whichever comes first) is not considered an AE. If any AEs are observed after the safety follow-up period has ended, only those AEs suspected to have a causal relationship with the study drug will be recorded in the CRF.

The analysis of AEs will be based on treatment-emergent adverse events.

Adverse drug reactions in this study are defined as adverse events (including laboratory abnormalities) determined to have a reasonable possibility of a causal relationship with the study drug.

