7.2.1. Adverse Events and Adverse Drug Reactions

- The number and proportion of subjects with adverse events and adverse drug reactions will be calculated by MedDRA SOC and PT and grade in each treatment arm. For grade 2 or higher events, grade 3 or higher events, and events with an incidence of $\geq 10\%$ in either arm (an incidence of $\geq 5\%$ for adverse drug reactions), the number and proportion of subjects will also be calculated by MedDRA SOC and PT and grade.
- According to ECOG PS entered in the CRF and age (< 75 years), the number and proportion of subjects with adverse events and adverse drug reactions will be calculated by MedDRA SOC and PT and grade in each treatment arm.
- The number and proportion of subjects with adverse events leading to discontinuation (subjects with adverse events recorded in “Treatment Discontinuation” of the CRF) will be calculated by MedDRA SOC and PT in each treatment arm.
- The number and proportion of subjects with adverse events leading to interruption of TAS-118 or S-1 within a cycle will be tabulated by MedDRA PT in each treatment arm.
- The number and proportion of subjects with adverse events leading to the interruption of L-OHP or CDDP will be tabulated by MedDRA SOC and PT in each treatment arm.
- The number and proportion of subjects with adverse events leading to a skip of L-OHP or CDDP will be tabulated by MedDRA SOC and PT in each treatment arm.
- The number and proportion of subjects with adverse events leading to dose reduction in TAS-118, S-1, L-OHP, or CDDP will be tabulated by MedDRA SOC and PT in each treatment arm.
- The number and proportion of subjects with adverse events leading to prolongation of the TAS-118 or S-1 recovery period will be tabulated by MedDRA SOC and PT in each treatment arm.
- The number and proportion of subjects with serious adverse events will be tabulated by MedDRA SOC and PT in each treatment arm. Serious adverse drug reactions will also be analyzed in the same manner.
- A list of adverse event type, grade, time of onset, causality, course, treatment, and other information will be created in the enrolled population.
- For serious adverse events, a list of grade, outcome, date of outcome, seriousness, causality, and other information will be created in the enrolled population.

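### Protocol 15.1.1 defines a related adverse event by timing alone, which neither complements its own definition of not related nor matches the SAP's definition of an adverse drug reaction

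*Protocol*

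**What the plan says.** Protocol 15.1.1 gives a two-category causality scale. On the first category it says "The AE is related if it follows a reasonable temporal sequence from administration of study medication". On the second it says "The AE is not related when there is no reasonable possibility that the study medication caused the event". It then explains that this wording "means there is no evidence to suggest a causal relationship between the drug and the adverse event and one or more of the following"; five conditions are listed, beginning with the disease under study and ending with an open category, Other.

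Protocol 15.1.2 defines adverse drug reactions (ADRs) separately: "Adverse drug reactions are concern noxious and unintended responses to a medicinal product within adverse events". It does not mention the related / not related scale. SAP 5.1.2.1 defines them as adverse events "determined to have a reasonable possibility of a causal relationship with the study drug".

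Both documents tabulate ADRs. Protocol 16.3.3.3 says "For adverse drug reaction, same analyses as adverse events will be performed". SAP 7.2.1 says "The number and proportion of subjects with adverse events and adverse drug reactions will be calculated by MedDRA SOC and PT and grade", by arm, and adds a table of ADRs with an incidence of at least 5% in either arm and a table of serious ADRs.

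The label is used elsewhere too. Protocol 10.1.3.3 opens with "If the patients suffered any adverse drug reaction that meets any of the following dose reduction criteria", and 10.1.3.4 uses the same construction for Arm B. Under Protocol 15.1.1, an event seen after the safety window is recorded only if it is judged causally linked to the drug.

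**The concern.** A two-category scale works only if every event falls in exactly one category. Here one category is defined by when the event happened and the other by whether the drug could have caused it. An investigator facing a symptom of the cancer that appears a few days after dosing can justify either code from the text.

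Such events will be collected. Protocol 15.1.4 requires the signs, symptoms and complications of progression to be reported as adverse events or serious adverse events, with a note of whether they relate to progression.

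At stake are the ADR and serious ADR tables by arm, and which late events are recorded. A site that reads the *related* rule literally will code more events as related than a site that works from the *not related* rule, and treatment is open-label, so blinding does not protect the coding. The analyst then receives a field coded under one rule and reports it under a definition worded differently, with no statement of which prevails.

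**Working it through.** The plan gives no figure to reproduce, so the check is one of logic.

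**1. Do the two rules partition events?** Classify an event by three features: plausible timing (T), evidence of causation other than timing (E), and a listed alternative explanation (A). The protocol does not say whether timing itself counts as evidence, so both readings are shown. The last column applies the fix proposed below.

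| T | E | A | Meets *related* | Meets *not related*, timing not evidence | Meets *not related*, timing is evidence | After fix |
|---|---|---|---|---|---|---|
| yes | yes | yes | yes | no | no | related |
| yes | yes | no | yes | no | no | related |
| yes | no | yes | **yes** | **yes** | no | not related |
| yes | no | no | yes | no | no | related |
| no | yes | yes | no | no | no | related |
| no | yes | no | no | no | no | related |
| no | no | yes | no | yes | yes | not related |
| no | no | no | no | no | no | related |

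The third row is the problem case: plausible timing, an alternative cause and nothing else pointing to the drug. If timing is not evidence, both definitions apply. If it is, the overlap goes, but the event must be coded related and the list of alternatives has no effect on it. In three rows (fifth, sixth and eighth) neither rule assigns a code. These are logical combinations, not frequencies.

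**2. Does the SAP match?** Reasonable possibility in SAP 5.1.2.1 is the converse of the protocol's *not related* rule, so those two agree. It conflicts only with the timing rule. The root of the problem is inside the protocol.

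**3. How well can timing discriminate?** On the nominal schedule, oral drug is given on 7 of 14 days in Arm A (Protocol 10.1.2.1) and 21 of 35 in Arm B (10.1.2.2, 10.1.2.3). The infusions fall within those days. For a window of W days after an oral dose, the share of cycle days covered is min(dosing days + W, cycle length) / cycle length. W is an assumption, because the protocol does not define a reasonable sequence.

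| W | Arm A | Arm B |
|---|---|---|
| 0 | 7/14 = 50% | 21/35 = 60% |
| 3 | 10/14 = 71% | 24/35 = 69% |
| 7 | 14/14 = 100% | 28/35 = 80% |
| 14 | 14/14 = 100% (capped) | 35/35 = 100% |

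Timing alone therefore separates little once the window reaches one to two weeks. These are shares of days, not of events or patients, and do not give a size for the effect.

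**The case against.** The strongest reply is that the two limbs are meant to be read together. The disease under study is the first listed alternative, so an event clearly due to the cancer has a natural home under *not related*. Protocol 15.1.1 already excludes symptoms of pre-existing disease unless they are new or worse. An ADR in 15.1.2 is a response to a product, which is a causal idea. The completion guidelines for the CRF and for serious events, which are not part of these documents, may settle the matter. All of this makes sensible coding likely. It does not remove the conflict: in the *related* rule the word reasonable qualifies the time sequence, not causation, and nothing says which limb prevails.

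The reply is right about reach. SAP 5.1.2.1 bases the adverse event analysis on treatment-emergent events whatever their cause. In SAP 7.2.1 the discontinuation, interruption, skip and dose-reduction tables count adverse events, not ADRs. Late serious events under Protocol 15.1.3 rest on what the investigator believes.

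Three stronger readings are tempting and are not supported:

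- A reader might infer that nearly every on-treatment event will be tabulated as an ADR. That is an upper bound under the most literal reading, not a prediction.
- A reader might try to size the inflation by assuming the share of events with a reasonable possibility of causation and inverting it. That only restates the assumption, and it counts events where SAP 7.2.1 counts subjects.
- A reader might infer bias between arms. The day shares above change direction with the window (Arm B higher at W = 0, Arm A higher at W = 3 and 7, equal at 14), and inconsistency between sites is not in itself a difference between arms.

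**Conclusion.** The point holds as a contradiction in definitions and should be corrected. The timing-only rule is not the complement of the protocol's *not related* rule and does not match the SAP's ADR definition. Applied literally, it can inflate the descriptive ADR and serious ADR tables, affect which late events are recorded, and let sites code the same event differently. The size cannot be derived from the documents. The conclusion rests on the printed definitions, and on no unseen guideline having already replaced them at the sites. Overall survival, the all-cause adverse event tables and the tables of events leading to treatment changes are unaffected.

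**What to change.** In Protocol 15.1.1, define *related* as a reasonable possibility that the study medication caused the event. State that temporal sequence is one supporting consideration, neither sufficient nor separately required. Keep the present *not related* definition, including its two safeguards (no evidence, and an alternative explanation), and say that it is the exact complement: any event that does not meet it is related.

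Simply adding reasonable possibility as a second condition beside timing, with everything else coded *not related*, would not do. The SAP has no timing condition, so a possible reaction with unusual timing would be an ADR in the SAP and unrelated in the protocol. That wording would also remove the safeguards before *not related* can be coded.

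In Protocol 15.1.2 and SAP 5.1.2.1, state that an ADR is an adverse event coded related on the CRF under this criterion, and name the field. In Protocol 10.1.3.3 and 10.1.3.4, only the terminology needs reconciling with that definition; no change to the dose rules is suggested.

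The cost is a few sentences, a site notice and an entry in the SAP change record. The protocol version is dated November 2019 and study treatment runs to 31 January 2020, so most events will already have been coded. For those, report with the ADR tables the wording under which they were classified.
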